8.1.2 Medical History

At Visit 1, each patient will be required to provide basic demographic information: date of birth, gender, ethnicity and race. Patients will also be questioned about medical history, including acute and chronic medical history and medical history relevant to their head lice.

Medical history data will be listed by treatment and patient.

8.1.3 Concomitant Medications

At Visit 1, patients will be questioned about current and previous medication use over the last four weeks. At all subsequent visits, patients will be questioned about ongoing or new concomitant medication use.

All prior and concomitant medications taken since screening until the end of the study will be listed by treatment and patient.

STATISTICAL ANALYSIS PLAN

Ivermectin Lotion 0.5%

Protocol / Study No. 71691702

8.1.4 Pregnancy Test

All females of childbearing potential will have a urine pregnancy test performed at each visit.

Pregnancy test results will be listed by treatment and patient.

8.2 Efficacy Analyses

8.2.1 Primary and Secondary Endpoint Analysis

Therapeutic Bioequivalence Analysis

The primary measure of therapeutic equivalence will be evaluated using the Per-Protocol population.

Based on the usual method used in OGD for binary outcomes, the 90% confidence interval for the difference in success proportions between test and reference treatment should be contained within [-0.20, +0.20] in order to establish equivalence.

The compound hypothesis to be tested is:

$$H_0: P_T - P_R \leq -.20 \text{ or } P_T - P_R \geq .20 \quad \text{versus}$$

$$H_A: -.20 < P_T - P_R < .20$$

where P_T = success rate of test treatment

P_R = success rate of reference treatment.

Let

n_T = sample size of test treatment group

cn_T = number of subjects considered as Treatment Success in test treatment group

n_R = sample size of reference treatment group

cn_R = number of subjects considered as Treatment Success in reference treatment group

$\hat{P}_T = cn_T/n_T$ $\hat{P}_R = cn_R/n_R$, and

$$se = (\hat{P}_T (1 - \hat{P}_T)/n_T + (\hat{P}_R (1 - \hat{P}_R)/n_R))^{1/2}$$

The 90% confidence interval for the difference in proportions between test and reference will be calculated as follows:

STATISTICAL ANALYSIS PLAN

Ivermectin Lotion 0.5%

Protocol / Study No. 71691702

$$L = (\hat{P}_T - \hat{P}_R) - 1.645 \text{ se}$$

$$U = (\hat{P}_T - \hat{P}_R) + 1.645 \text{ se}$$

If the 90% confidence interval for the absolute difference between the proportion of patients who are considered a Treatment Success in the Test and Reference groups is contained within the range [-20%, +20%] then therapeutic equivalence of the Test product to the Reference product will be considered to have been demonstrated.

The same statistical approach will be conducted for analysis of the secondary endpoint in the PP population.

To declare therapeutic equivalence of the Test product to the Reference product, therapeutic equivalence must be demonstrated for only the primary endpoint in the PP population.

Superiority to Placebo Analysis

Superiority of the Test and Reference products against the Placebo for the primary endpoint will be tested at the 5% significance level ($p < 0.05$; two-sided, CMH test, stratified by clinical site) in the mITT population using last observation carried forward (LOCF). If the proportions of patients who are considered a Treatment Success in the Test and Reference groups are numerically and statistically superior to that of the Placebo ($p < 0.05$; using two-sided, CMH test stratified by clinical site), then superiority of the Test and Reference products over Placebo will be concluded.

The same statistical approach will be conducted for analysis of the secondary endpoint in the mITT population.

To declare superiority of the Test and Reference products over Placebo, their superiority must be demonstrated for only the primary endpoint in the mITT population.

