Evaluation of Therapeutic Equivalence and Superiority	
Therapeutic Equivalence Analysis
 
Therapeutic equivalence will be evaluated for both primary and secondary endpoints using the per-protocol (PP) population. If the 90% confidence interval for the absolute difference between the proportion of patients who are considered a Treatment Success in the Test and Reference groups is contained within the range [-20%, +20%] then therapeutic equivalence of the Test product to the Reference product will be considered to have been demonstrated.
 
The same statistical approach will be conducted for analysis of the secondary endpoint in the PP population.
 
To declare therapeutic equivalence of the Test product to the Reference product, therapeutic equivalence must be demonstrated for only the primary endpoint in the PP population.
 
Superiority Analysis
 
Superiority of the Test and Reference products against the Placebo for the primary endpoint will be tested at the 5% significance level ($p < 0.05$; two-sided, Cochran-Mantel-Haenszel (CMH) test, stratified by clinical site) in the mITT population using last observation carried forward. If the proportions of patients who are considered a Treatment Success in the Test and Reference groups are numerically and statistically superior to that of the Placebo ($p < 0.05$; using two-sided, CMH test stratified by clinical site), then superiority of the Test and Reference products over Placebo will be concluded.
 
The same statistical approach will be conducted for analysis of the secondary endpoint in the mITT population.
 
To declare superiority of the Test and Reference products over Placebo, their superiority must be demonstrated for only the primary endpoint in the mITT population. The superiority testing will treat all patients who have no

[figure not shown]
CONFIDENTIAL PROTOCOL

A Randomized, Double-Blind, Placebo-Controlled, Parallel-Design, Multiple-Site Clinical Study to Evaluate the Therapeutic Equivalence and Safety of Ivermectin Lotion 0.5% (Actavis Laboratories UT, Inc.) to SKLICE® (ivermectin) Lotion, 0.5% (Arbor Pharmaceuticals, LLC) in the Treatment of Human Head Lice Infestation

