	
data on Day 15 as treatment failure.
 
Treatment-by-Site Interaction and Pooling of Clinical Sites
 
As this is a multiple-site study, the interaction of treatment-by-site may be evaluated for the primary efficacy endpoint in the PP population (for equivalence testing). The treatment-by-site interaction will be evaluated by the Breslow-Day test for homogeneity of the odds ratio at the 5% significance level ($p < 0.05$). A site(s) with a low enrollment rate(s) may be pooled with its geographically closest site, so as to avoid bias in the estimation of a treatment-by-site interaction effect. The pooling will be done for low enrolling sites that account for less than 4-7% of the total number of patients in the PP population at the site with the highest enrolling rate in the PP population. If the treatment-by-site interaction term is found to be statistically significant ($p < 0.05$) then the interaction term will also be assessed for clinical relevance before pooling the data across sites. This will include examination of Treatment Success rates at each site where sample sizes per treatment may be influential in the assessment of the interaction.

Safety Analysis	
Adverse events (AEs) will be classified using standard Medical Dictionary for Regulatory Activities (MedDRA) terminology Version 20.0 or higher and summarized by treatment group. Summary tables comparing the type, date of onset, date of resolution, incidence, severity, relationship to the study product, action taken, and outcome will be prepared by treatment group. If sufficient data exist, then AE frequencies will be compared among treatments using Fisher's exact test or a similar test. Application site reactions and ocular discomfort will be compared descriptively among treatment groups.
 
Concomitant medication use during the randomized treatment period will be tabulated by patient.
 
Signs and symptoms of head lice will not be considered AEs, unless in the Investigator's opinion, they have increased in frequency and/or severity to such an extent that the Investigator/patient considers to be clinically significant.
 
All patients who are randomized and received study product will be included in the comparative safety analysis.

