4. RANDOMIZATION AND BLINDING

The study product will be randomized, packaged and blinded by an independent packaging company (Actavis, SLC site). The randomization will be pre-planned according to a computer-generated randomization schedule. All enrolled members of a household will be randomized to the same treatment arm.

Using [REDACTED] Interactive Web Response Technology System (IWRS), all eligible and non-eligible patients who are consented and screened into the study will be assigned a patient number. The patient number is assigned after a patient is consented. It is the only identifier for screened patients.

[REDACTED] The system will also assign a study product kit number (based on the randomization schedule created by an independent biostatistician). The study product kit number is the identifying number listed on the study product dispensed to eligible patients. The study product kit number is a five-digit number. This will be the identifier used for randomized patients (i.e., randomization number). Both the patient number and randomization number will be entered into the patient's eCRF. At the end of the study, after all the clinical data have been entered and the study database has been locked, a copy of the randomization schedule will be sent to the statistician.

The Investigator, staff at the study site, study monitors, and data analysis/management personnel will be blinded to the patient assignment.

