6. ANALYSIS POPULATION

Per-Protocol Population (PPP)

The PP population will include all randomized patients who:

- Meet all inclusion and exclusion criteria.
- [REDACTED]
- [REDACTED]
- Have no significant protocol deviations.
- Apply the study product as instructed on Day 1.

STATISTICAL ANALYSIS PLAN

Ivermectin Lotion 0.5%

Protocol / Study No. 71691702

Modified Intent-to-Treat Population (mITT)

The mITT population will include all randomized patients who meet all inclusion/exclusion criteria, apply the study product as instructed, and return for at least one post-baseline evaluation visit.

Safety Population

The Safety population will include all patients who are randomized and received study product.

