7. EFFICACY ENDPOINTS

Primary Efficacy Endpoint

The primary efficacy endpoint is the proportion of index patients in each treatment group who are considered a Treatment Success on Day 15 ± 2 . Treatment Success is defined as the absence of live lice.

Secondary Efficacy Variable

The secondary efficacy endpoint is the proportion of all randomized patients (i.e., index + non-index) who are considered a Treatment Success on Day 15 ± 2 . Treatment Success is defined as the absence of live lice.

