Reference: SKLICE® (ivermectin) Lotion, 0.5% (Arbor Pharmaceuticals, LLC)

Placebo: Placebo (vehicle) lotion (Actavis Laboratories UT, Inc.)

OUTPUT: L:\DEV\917\71691702\SAS\OUT\XXXX

Created on: ddmmmyy hh:mm

Page 1 of N

01/12/2017

■ Actavis LLC■

Page 29 of 52

STATISTICAL ANALYSIS PLAN

Ivermectin Cream 0.5%

Protocol / Study No. 71691702

T16.1.9.8 Summary of Analysis Results of Secondary Efficacy Endpoint (Proportion of All Randomized Patients with Treatment Successes between Treatment Groups)

Equivalence: Per-Protocol Population

Treatment Group	Number of Patients (N)	Number of Treatment Successes (n)	Proportion of Treatment Successes (%)	Difference Between Treatments	
				Difference (%)	90% CI Evaluation
Test	xxx	xxx	xx.x		
Reference	xxx	xxx	xx.x	xx.x	xx.x – xx.x

Superiority: modified Intent-to-Treat Population

Treatment Group	Number of Patients (N)	Number of Treatment Successes (n)	Proportion of Treatment Successes (%)	P-value
Placebo	xxx	xxx	xx.x	
Test	xxx	xxx	xx.x	x.XXXX
Reference	xxx	xxx	xx.x	x.XXXX

Superiority of Active treatments over Placebo were tested using a two-sided Cochran-Mantel-Haenszel(CMH) test, stratified by clinical site, at the 5% significance level.

Test: Ivermectin Lotion, 0.5% (Actavis Laboratories UT, Inc.)

Reference: SKLICE® (ivermectin) Lotion, 0.5% (Arbor Pharmaceuticals, LLC)

Placebo: Placebo (vehicle) lotion (Actavis Laboratories UT, Inc.)

OUTPUT: L:\DEV\917\71691702\SAS\OUT\XXXX

Created on: ddmmmyy hh:mm

Page 1 of N

01/12/2017

■ Actavis LLC■

Page 30 of 52

STATISTICAL ANALYSIS PLAN**Ivermectin Cream 0.5%****Protocol / Study No. 71691702****T16.1.9.9 Overall Summary of Adverse Events
(Safety Population)**

Description	Test	Reference	Placebo	Total
Patients Randomized	xxx	xxx	xxx	xxx
Patients with at least one AE	xx (xx.x%)	xx (xx.x%)	xx (xx.x%)	xx (xx.x%)
Discontinued study drug due to above AE	xx (xx.x%)	xx (xx.x%)	xx (xx.x%)	xx (xx.x%)
AEs reported	xxx	xxx	xxx	xxx
Mild	xx (xx.x%)	xx (xx.x%)	xx (xx.x%)	xx (xx.x%)
Moderate	xx (xx.x%)	xx (xx.x%)	xx (xx.x%)	xx (xx.x%)
Severe	xx (xx.x%)	xx (xx.x%)	xx (xx.x%)	xx (xx.x%)
Not Related	xx (xx.x%)	xx (xx.x%)	xx (xx.x%)	xx (xx.x%)
Related	xx (xx.x%)	xx (xx.x%)	xx (xx.x%)	xx (xx.x%)
Death	xx (xx.x%)	xx (xx.x%)	xx (xx.x%)	xx (xx.x%)
Serious AE	xx (xx.x%)	xx (xx.x%)	xx (xx.x%)	xx (xx.x%)

Test: Ivermectin Lotion, 0.5% (Actavis Laboratories UT, Inc.)

Reference: SKLICE® (ivermectin) Lotion, 0.5% (Arbor Pharmaceuticals, LLC)

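### The secondary endpoint counts several members of one household as independent patients, although the household is assigned to treatment as a unit

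*SAP*

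**What the plan says.** SAP section 4 makes the household the unit of assignment: "All enrolled members of a household will be randomized to the same treatment arm". Exclusion criterion 4 (Protocol 10.3.2) allows at most three infested members, and every participant must be infested, so a household contributes one to three patients.

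SAP section 7 defines the secondary endpoint as "the proportion of all randomized patients (i.e., index + non-index") with no live lice on Day 15 ± 2. The primary endpoint uses index patients only, one per household.

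SAP 8.2.1 builds the equivalence interval from counts of subjects, with variance P(1−P)/n in each arm and a multiplier of 1.645. For the secondary endpoint it adds "The same statistical approach will be conducted for analysis of the secondary endpoint in the PP population" and, for superiority, "The same statistical approach will be conducted for analysis of the secondary endpoint in the mITT population". The footnote of shell T16.1.9.8 says superiority is "tested using a two-sided Cochran-Mantel-Haenszel(CMH) test, stratified by clinical site". Protocol 11.6 and the synopsis are worded to the same effect. No visible text in either document adds a household term, and SAP 8.4 and 8.5 do not mention one.

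Three further statements determine how many household members count:

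- Protocol 10.5.2 says treated household members come back for Visit 2 only, although the endpoint needs a Day 15 result.
- The mITT population requires only that a patient "return for at least one post-baseline evaluation visit", and SAP 8.2.1 applies LOCF.
- The protocol synopsis alone gives a failure rule: "The superiority testing will treat all patients who have no" "data on Day 15 as treatment failure".

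**The concern.** Members of a household share the arm, the home and the exposure to re-infestation, so their outcomes are likely to be positively correlated. Treatment does not vary within a household, so that correlation adds directly to the variance of the difference between arms. The binomial formula and the CMH variance both leave it out.

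What is at stake is the accuracy of table T16.1.9.8. Its interval would claim more precision than the data hold wherever several members per household are observed. Its p-values would be off in a direction that depends on follow-up and on the missing-data rule.

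**Working it through.** **The plan's own figure.** 2Φ(1.645) − 1 = 0.900, so the planned interval has its nominal level when patients are independent. Simulation with one patient per household gives 89–90% coverage and a CMH size of 4.9–5.2%.

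**Inputs.** From the documents: about 378 index patients (protocol synopsis), at most three patients per household, the 1.645 interval, and the site-stratified CMH test at 5%. Assumed, because they are redacted or not given: equal allocation, hence 378/3 = 126 households per arm; 10 sites; 75% success; the intraclass correlation (ICC); and the household sizes. Mix A has one, two or three patients in 60/30/10% of households, and mix B in 40/35/25%. All test sizes are for equal true success in the two arms compared.

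**Formulas.** For household size m:

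- design effect DE = 1 + (E[m²]/E[m] − 1) × ICC
- true coverage = 2Φ(1.645/√DE) − 1
- true size = 2[1 − Φ(1.96/√DE)]

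Mix A: E[m] = 1.50, E[m²] = 2.70, ratio 1.80. Mix B: E[m] = 1.85, E[m²] = 4.05, ratio 2.19. All households of three: ratio 3.

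**All members examined at Day 15**

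| ICC | Mix A: DE | coverage | size | Mix B: DE | coverage | size | All threes: DE | coverage | size |
|---|---|---|---|---|---|---|---|---|---|
| 0.05 | 1.04 | 89.3% | 5.5% | 1.06 | 89.0% | 5.7% | 1.10 | 88.3% | 6.2% |
| 0.1 | 1.08 | 88.7% | 5.9% | 1.12 | 88.0% | 6.4% | 1.20 | 86.7% | 7.4% |
| 0.2 | 1.16 | 87.3% | 6.9% | 1.24 | 86.1% | 7.8% | 1.40 | 83.6% | 9.8% |
| 0.4 | 1.32 | 84.8% | 8.8% | 1.48 | 82.4% | 10.7% | 1.80 | 78.0% | 14.4% |
| 0.6 | 1.48 | 82.4% | 10.7% | 1.71 | 79.1% | 13.4% | 2.20 | 73.3% | 18.6% |

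Beta-binomial simulation with the planned interval and CMH test agrees to within about 1.5 points.

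**Interval width, mix B, ICC 0.4.** Patients per arm: 126 × 1.85 = 233. Planned half-width: 1.645 × √(2 × 0.75 × 0.25/233) = 6.6 points. Clustered half-width: 6.6 × √1.476 = 8.0 points. Against the 20-point margin, the equivalence reading differs only for an observed difference between 20 − 8.0 = 12.0 and 20 − 6.6 = 13.4 points.

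**Partial Day 15 follow-up, unobserved patients left out (PP interval, mix B, ICC 0.1/0.4/0.6, simulated).** Coverage is 89.0/84.8/83.0% with half of the non-index patients observed and 89.1/87.8/86.4% with a quarter. With none observed it is 89.5–89.8%, so there is no effect.

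**LOCF (mITT).** Suppose every non-index patient carries a Day 2 status, with assumed Day 2/Day 15 success of 90/75, 80/75, 50/30 or 35/30%. Simulated CMH size over mixes A and B is 5.1–6.3% at ICC 0.1, 6.7–10.4% at 0.4 and 7.9–12.6% at 0.6.

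**Failure rule (mITT, mix B).** With half of the non-index patients set to failure, simulated size is about 4% at ICC 0.1 and 6% at ICC 0.4. With all set to failure it is about 1.5% whatever the ICC, because only the index outcome then varies.

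**The case against.** The strongest case against is about weight. Both declarations rest on the primary endpoint, which is unaffected. At ICC 0.05–0.1 the excess size is about 1 point or less for mix A and at most about 1.5 points for mix B. The equivalence reading changes only in a band of 1.4 points. For superiority at mix B and ICC 0.4, only a naive p-value between about 0.017 and 0.05 would lose significance (1.96 × √1.476 = 2.38, two-sided p = 0.017). If the primary superiority result holds, the secondary null hypothesis is probably false anyway. All of this stands, and it limits the point to the accuracy of secondary results.

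It is also fair that the size and, for the CMH test, the direction cannot be settled from the public text. The ICC and household sizes are not given, and some definitions and PP criteria are redacted. If the Visit 2 statement in Protocol 10.5.2 covers enrolled non-index patients, few of them would have Day 15 data. The conflicts over follow-up and missing data are separate defects that would remain after the variance is corrected.

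None of this rescues the formula. SAP 8.2.1 is legible on the method and has no household term. The planned variance is right only if outcomes within households are uncorrelated or each household supplies one observed outcome, and the SAP states neither.

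**Conclusion.** The concern holds. The secondary analysis uses a patient-level variance for a comparison assigned by household. Where several members have observed, positively correlated outcomes, the nominal 90% interval covers about 89% at ICC 0.05 and 79–82% at ICC 0.6 (mixes A and B), and the 5% CMH test has a true size of about 5.5% rising to 11–13%. The superiority test is too liberal under LOCF if Day 2 statuses are correlated. It falls to or below its nominal size if most non-index patients are set to failure.

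These sizes rest on the assumed ICC, household mix and success rates; the missing household term does not. The cap of three patients per household keeps the design effect at or below 3. The primary analysis and both formal declarations are unaffected. The change should be made, but the trial's main conclusions do not depend on it.

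**What to change.** For the secondary endpoint only, replace the reference to the primary method in SAP 8.2.1 with the following.

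1. **Equivalence interval.** Difference in patient-level proportions ± 1.645 × SE, where SE² is the sum over the two arms of [H/(H−1)] × Σ_h (x_h − p·m_h)² / n². Here x_h and m_h are the successes and patients in household h, p is the arm's proportion, and H and n are its households and patients.
2. **Superiority test.** Keep the CMH numerator and replace its variance by the sum over sites of [H_s/(H_s−1)] × Σ_h u_h², with u_h = (a_h − n_as/n_s)(x_h − p_s·m_h). Here a_h is 1 for active and 0 for placebo; H_s, n_as, n_s and p_s are the households, active-arm patients, all patients and pooled success proportion at site s in the two arms compared. Refer numerator²/variance to chi-square with 1 df. State that a site with a single household in the comparison drops out; its numerator and every u_h are zero.

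Neither step needs an assumed ICC. With 10 sites, simulated coverage was 89.0–90.8% and size 4.4–5.8%, including under LOCF and failure imputation for the test. With 20 very uneven sites, size reached 6.1%.

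Also:

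- Correct the T16.1.9.8 footnote and carry a household identifier in the analysis dataset.
- Reconcile Protocol 10.5.2 with the Day 15 endpoint, and state how many non-index patients are expected to have a Day 15 examination.
- State whether LOCF or the failure rule applies to them.

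The cost is SAP wording, one footnote, one variable and a short program, all before database lock. Protocol 11.6 and the synopsis can be aligned at the next amendment, since a protocol change needs IRB review. Secondary intervals widen by √DE − 1 for ICC 0.05–0.6: 2–22% (mix A) or 3–31% (mix B), and by just under 50% if every household has three patients and the ICC is 0.6. The primary analysis stays as it is.

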8.2.2 Treatment-by-Site Interaction and Pooling of Clinical Sites

As this is a multiple-site study, the interaction of treatment-by-site may be evaluated for the primary efficacy endpoint in the PP population (for equivalence testing). The treatment-by-site interaction will be evaluated by the Breslow-Day test for homogeneity of the odds ratio at the 5% significance level ($p < 0.05$). A site(s) with a low enrollment rate(s) may be pooled with its geographically closest site, so as to avoid bias in the estimation of a treatment-by-site interaction effect. The pooling will be done for low enrolling sites that account for less than 4-7% of the total number of patients in the PP population at the site with the highest enrolling rate in the PP population. If the treatment-by-site interaction term is found to be statistically significant ($p < 0.05$) then the interaction term will also be assessed for clinical relevance before pooling the data

STATISTICAL ANALYSIS PLAN

Ivermectin Lotion 0.5%

Protocol / Study No. 71691702

across sites. This will include examination of Treatment Success rates at each site where sample sizes per treatment may be influential in the assessment of the interaction.

